3.6.2.2. Hamilton Rating Scale for Anxiety (HAM-A)

The HAM-A is a clinician-administered 14-item scale developed to measure the severity of anxiety symptoms. The HAM-A total score is the sum of all 14 items and ranges from 0 to 56. Section 6.2 describes the handling of total score if any of the items of the HAM-A is missing.

The following endpoints will be assessed

- Change from baseline in HAM-A total score
- Change from baseline in HAM-A psychic subscale, where the psychic subscale is the sum of HAM-A items 1 to 6, and item 14
- Change from baseline in HAM-A somatic subscale, where the somatic subscale is the sum of HAM-A items 7 to 13

Descriptive summary statistics of baseline, HAM-A total score and change from baseline at each visit including the last assessment during treatment period will be provided by prior ALKS 5461 exposure and overall based on observed data. The HAM-A psychic subscale and somatic subscale will be summarized in a similar way. In addition, a figure of HAM-A total score (including standard error), mean change from baseline (including standard error) over time including the last assessment during treatment period will be provided by prior ALKS 5461 exposure and overall.

The individual HAM-A item score will not be summarized but will be included in the subject listing.

3.6.2.3. Clinical Global Impression – Severity (CGI-S)

The CGI-S is a 7-point scale that requires the clinician to rate the severity of the subject's illness at the time of assessment, relative to the clinician's past experience with subjects who have the same diagnosis. Considering total clinical experience, a subject is assessed on severity of mental illness at the time of rating 0=not assessed; 1=normal, not at all ill; 2=borderline mentally ill; 3= mildly ill; 4=moderately ill; 5=markedly ill; 6=severely ill; or 7=extremely ill. The rating of 0 (not assessed) will be considered as missing.

Descriptive summary statistics of baseline, CGI-S score and change from baseline at each visit including the last assessment during treatment period and follow up period will be provided by prior ALKS 5461 exposure and overall based on observed data. The number and percentage of subjects for each CGI-S category at each visit including the last assessment during treatment period and follow up period will also be summarized. In addition, figures of CGI-S score (including standard error) and mean change from baseline (including standard error)over time including the last assessment during treatment period and follow up period will be provided by prior ALKS 5461 exposure and overall based on observed data.

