8.2. Schedule of Visits and Assessments

The schedule of visits and assessments is shown in [Table 2](#) for screening through the treatment period, and in [Table 3](#) for the safety follow-up period.

For a missed visit, the site should attempt to contact the subject to reschedule.

Subjects who discontinue from the study prematurely will be encouraged to return for an early termination (ET) visit and to participate in a subsequent follow-up period. The Visit 14 assessments will serve as early termination assessments for any subject who withdraws prior to completion. The safety follow-up period for subjects who discontinue early should mirror the visits displayed in [Table 3](#).

Table 2: Schedule of Visits and Assessments, Screening and Treatment Period

Evaluation	Screening ^a	ALKS 5461 Treatment Period												
		Base-line	Week 1	Week 2	Week 4	Week 6	Week 8	Week 14	Week 20	Week 26	Week 32	Week 38	Week 44	Week 52
Study Day:	-28 to -1	1	8 (±1)	15 (±1)	29 (±3)	43 (±3)	57 (±3)	99 (±3)	141 (±3)	183 (±3)	225 (±3)	267 (±3)	309 (±3)	ET/365 ^b (±3)
Visit Number:	1	2 ^c	3	4	5	6	7	8	9	10	11	12	13	14
Informed Consent ^d	X													
Qualification/ Diagnostic Assessments														
Eligibility Criteria Review	X	X ^e												
Demographics	X													
Medical/ Psychiatric History	X	X ^e												
Serology Testing ^f	X													
ATRQ	X													
MINI	X													
Breath Alcohol Test ^g	X													
Height	X													
Full Physical Examination	X													
HAM-D	X	X ^e												
Qualification/ Safety Assessments														
Weight/ Vital Signs ^h	X	X ^e	X	X	X	X	X	X	X	X	X	X	X	X
12-lead ECG	X	X ^e	X							X				X
Drug Screening ⁱ	X	X ^e	X					X		X		X		X
Pregnancy Testing ^j	X	X ^e						X		X		X		X
Symptom-Directed Physical Examination		X												X

Table 2: Schedule of Visits and Assessments, Screening and Treatment Period (Continued)

Evaluation	Screening ^a	ALKS 5461 Treatment Period												
		Base-line	Week 1	Week 2	Week 4	Week 6	Week 8	Week 14	Week 20	Week 26	Week 32	Week 38	Week 44	Week 52
Study Day:	-28 to -1	1	8 (±1)	15 (±1)	29 (±3)	43 (±3)	57 (±3)	99 (±3)	141 (±3)	183 (±3)	225 (±3)	267 (±3)	309 (±3)	ET/365 ^b (±3)
Visit Number:	1	2 ^c	3	4	5	6	7	8	9	10	11	12	13	14
Blood and Urine Samples for Safety Labs	X	X ^c	X					X		X		X		X
C-SSRS ^k	X	X ^c	X	X	X	X	X	X	X	X	X	X	X	X
COWS ^l														X
Adverse Event Monitoring	X	X	X	X	X	X	X	X	X	X	X	X	X	X
Concomitant Medication Review ^m	X	X	X	X	X	X	X	X	X	X	X	X	X	X

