2. SAMPLE SIZE AND STATISTICAL POWER CONSIDERATION

Approximately 1,500 subjects will be enrolled in order to achieve at least 100 subjects with 12 months and 300 subjects with 6 months of exposure to ALKS 5461. Subjects will enter from four feeder studies or enter de novo. The antecedent studies included ALK5461-205, ALK5461-206, ALK5461-207, and ALK5461-210.

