3.7.5. Vital Signs

Vital signs (supine systolic and supine diastolic blood pressure, heart rate, respiratory rate, temperature, weight, and BMI) will be summarized for baseline and change from baseline (BMI baseline only) by prior ALKS 5461 exposure and overall for the Safety Population, and will include post-discontinuation assessments.

In addition, baseline and post-baseline observed values (lowest, highest, last assessment during treatment period), and change from baseline to lowest, highest and last assessment values during treatment period for vital sign parameters will be summarized by prior ALKS 5461 exposure and overall for the Safety Population, and will not include post-discontinuation assessments.

The following graphical displays for vital sign parameters will be presented by prior ALKS 5461 exposure and overall for the Safety Population:

- Line graphs for mean change from baseline along with the corresponding SE (including Post-discontinuation Safety Period)
- Box-and-Whisker figures for baseline and post-baseline observed values (lowest, highest, and last assessment during treatment period)
- Box-and-Whisker figures for change from baseline to the lowest post-baseline value, the highest post-baseline value, and the last scheduled post-baseline value during treatment period
- Scatter plots for baseline and post-baseline observed values (lowest, highest, and last assessment during treatment period)

Vital signs will also be evaluated using PCS criteria as indicated in Table 8 and summarized by prior ALKS 5461 exposure and overall for the Safety Population. Post-discontinuation assessments will not be included in this analysis.

 Table 8:
 Potentially Clinically Significant Abnormal Vital Sign Values

Parameter	PCS Criteria	
Temperature	Hyperthermia: ≥38.1°C	
	Hypothermia: ≤35.0°C	
Supine Systolic Blood Pressure	Low: ≤90 mm Hg and decrease ≥20 mm Hg	
	High: ≥140 mm Hg and increase ≥20 mm Hg	
Supine Diastolic Blood Pressure	Low: ≤50 mm Hg and decrease ≥10 mm Hg	
	High: ≥90 mm Hg and increase ≥10 mm Hg	
Heart Rate	Low: ≤50 bpm and decrease ≥15 bpm	
	High: ≥100 bpm and increase ≥15 bpm	
Respiratory Rate	Low: <12 breaths per minute	
	High: >25 breaths per minute	
Body Weight	Decrease from baseline ≥7%	
	Increase from baseline ≥7%	

A supportive listing will present for subjects and parameter for cases where at least 1 value was potentially significant.

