3.7.8. Clinical Opiate Withdrawal Scale (COWS) Scores

COWS will be administered only at EOT and post-discontinuation visits, so COWS will be analyzed for Post-discontinuation Safety Population. For Post-discontinuation Safety Population, baseline COWS is defined as EOT COWS assessment. Adequate COWS baseline is defined as EOT COWS assessment being performed within (\leq) 2 days of last dose of study drug.

Subjects will be included in the COWS analysis if they have an adequate EOT COWS and at least 1 post-EOT COWS in the post-discontinuation safety period. COWS will be summarized by:

- Analysis of all post-EOT COWS assessments
- Analysis of post-EOT COWS assessments that occurred from >2 to 16 days post last dose of study drug

Subjects with inadequate EOT COWS, i.e. EOT COWS assessment was performed more than (>) 2 days of last dose, will be included in a supportive listing.

Although opioid withdrawal might not be expected in individuals with less than 4 weeks of drug exposure, COWS will be presented in all subjects with adequate EOT COWS, and then COWS will be subset by duration of study drug exposure. Three COWS analyses will be presented for the subjects with adequate EOT COWS by the 3 exposure subgroups (any exposure, ≥4 weeks exposure, <4 weeks exposure):

- Total COWS scores (baseline and change from baseline, and days between last dose and assessment date) will be summarized by visit (baseline, post-discontinuation visits)
- Subject count and incidence will be provided by visit for each of the COWS total score categories indicated below:

No withdrawal: total score 0-4

Mild withdrawal: total score 5-12

Moderate withdrawal: total score 13-24

Moderately severe withdrawal: total score 25-36

- Severe withdrawal: total score >36

COWS category shift summary from baseline to post-baseline: the numerator is the
number of subjects in each post-discontinuation COWS category with non-missing
baseline COWS. If there are more than one post-discontinuation COWS, i.e. a subject
with an unscheduled visit, the highest value will be used. The denominator is the
number of subjects in each baseline COWS category.

Data listing of COWS scores at each visit will be provided. Narratives will be provided for any clinically meaningful COWS shifts.

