6.1. Analysis Visit Windows

Every attempt must be made to provide complete data. In cases where complete data cannot be collected, the principles to assign the analysis visits for inclusion in summary tables described in this section will be followed for data handling and analyses.

Early termination visits for efficacy measurements will be mapped to the next scheduled visit. For example, a subject who terminates shortly after Day 29 (e.g., has assessments at baseline through Day 29, and Day 365 or early termination) would have assessments at early termination mapped to the next scheduled visit for each assessment. In this example, the MADRS and CGI-S from the early termination visit would be mapped to Day 43; and the HAM-A results would be mapped to Day 57. For other visits other than early termination / Day 365, the visit number indicated on the CRF (i.e., CRF visit) will be used as the analysis visit.

Early termination visits for safety measurements will not be mapped to any scheduled post-baseline visit, but will be used as the last assessment during treatment period.

Measurements collected from unscheduled visits will not be included in the by-visit summary tables or mean change analyses but will be included in the analysis of outlier and PCS values and in the subject listings.

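### By-visit laboratory, vital-sign, ECG and CGI-S results use different sets of subjects at Week 52 and at follow-up, so who attends can create or hide an apparent shift after treatment stops

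*SAP*

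**What the plan says.** **Series that run through follow-up.** For CGI-S, SAP Section 3.6.2.3 says that "CGI-S score and change from baseline at each visit including the last assessment during treatment period and follow up period will be provided", with figures over the same span. For vital signs, Section 3.7.5 asks for "Line graphs for mean change from baseline along with the corresponding SE (including Post-discontinuation Safety Period". Sections 3.7.4.1 (laboratory) and 3.7.6 (ECG) ask for the same kind of by-visit summary and graph. All use observed data. The baseline is Visit 2 or earlier; for CGI-S in previously exposed subjects it is the value before dosing in the antecedent study (Section 3.2.1 and Table 2).

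**Where early termination visits go.** Section 6.1 treats the two kinds of endpoint differently:
- Safety: "Early termination visits for safety measurements will not be mapped to any scheduled post-baseline visit". These values serve only as the last on-treatment assessment.
- Efficacy: "Early termination visits for efficacy measurements will be mapped to the next scheduled visit".
- Visits other than early termination or Day 365: "the visit number indicated on the CRF (i.e., CRF visit) will be used as the analysis visit". This sentence follows the efficacy rule, but the SAP gives no other rule for Visits 15 to 18.

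**Who attends follow-up.** Protocol Section 8.2 says: "The safety follow-up period for subjects who discontinue early should mirror the visits displayed in" Table 3. Sections 7.3 and 8.2 ask or encourage early terminators to attend; they do not assure it. Table 3 schedules CGI-S at Visits 16 to 18, vital signs and weight at Visits 15 to 18, and laboratory tests and ECG at Visit 18 only.

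**The exception.** In Section 3.7.8, "For Post-discontinuation Safety Population, baseline COWS is defined as EOT COWS assessment". No comparable end-of-treatment baseline is planned for the other four endpoint groups.

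**The concern.** The step from Week 52 to follow-up is where a reader looks for rebound after stopping, or for reversal of a weight, laboratory or QTcF effect. The set of subjects changes at exactly that step, and each value is still expressed against a baseline a year or more earlier for completers. A difference between two groups of people can therefore be read as a change over time.

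This matters most for CGI-S, the only depression severity scale in the follow-up schedule: MADRS and HAM-A are not in Protocol Table 3. Discontinuation reasons in Protocol Section 7.3 include adverse events and lack of efficacy, so a difference between early terminators and completers is plausible, though the documents do not quantify it.

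**Working it through.** **1. The plan's own figure.** Section 2 of the SAP says: "Approximately 1,500 subjects will be enrolled in order to achieve at least 100 subjects with 12 months and 300 subjects with 6 months". This implies retention of at least 100/1,500 = 6.7% at 12 months and 300/1,500 = 20% at 6 months. These are minimum exposure targets, not expected completion rates. No dropout rate is stated, so 1,500 cannot be reproduced and the completer share must be assumed.

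**2. Who is in each point.**
- Week 52, laboratory, vital signs and ECG: subjects with a Day 365 visit.
- Week 52, CGI-S: those subjects plus any who stopped after Visit 13 (Day 309).
- Visits 15 to 18: completers plus returning early terminators, whenever they stopped.
- Last-assessment row: completers and early terminators, whether or not they return.

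**3. Formula.** Freeze every subject at the last on-treatment value, so the true post-treatment change is zero. Let C be completers (all assumed to attend), T early terminators, a the fraction of T who attend follow-up, and L the terminators mapped to Day 365 (zero for safety data). Let d be the mean difference, terminators minus completers, assumed the same for returning and mapped terminators. Then

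follow-up mean − Week 52 mean = d × [Ta/(C + Ta) − L/(C + L)].

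For safety data this is s × d, with s = Ta/(C + Ta).

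**4. Numbers.** The documents give none of C, a, L or d. Apparent shift, in units of d, for 1,500 subjects:

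| Endpoint | Completers | a = 10% | 30% | 60% | 100% |
|---|---|---|---|---|---|
| Safety (L = 0) | 30% | 0.19 | 0.41 | 0.58 | 0.70 |
| Safety (L = 0) | 50% | 0.09 | 0.23 | 0.38 | 0.50 |
| Safety (L = 0) | 70% | 0.04 | 0.11 | 0.20 | 0.30 |
| CGI-S (L = 10% of T) | 50% | 0.00 | 0.14 | 0.28 | 0.41 |

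Worked case, 50% completers and a = 60%: 450/(750 + 450) = 0.375 for safety data. For CGI-S, subtract 75/(750 + 75) = 0.091 to get 0.284. With an assumed d of 2 kg in weight change, the shift is 0.375 × 2 = 0.75 kg. With an assumed d of 1.2 CGI-S points, it is 0.284 × 1.2 = 0.34 points.

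At the 6.7% planning floor the safety shift would be 0.58d to 0.93d. If no terminator returned, the safety shift would be zero and the CGI-S shift would be −0.09d at 50% completers.

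**5. The last-assessment row as comparator.** Its mean lies d × T/(C + T) above the completer mean, which is 0.50d at 50% completers. Follow-up minus this row is zero if both groups attend equally. At a = 30% it is 0.23d − 0.50d = −0.27d, while follow-up minus Week 52 is +0.23d. The two comparators then disagree in sign, although nobody changed.

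**6. Same-subject change.** The change from each subject's own last on-treatment value is exactly zero in every scenario above, as it should be.

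**The case against.** The case against giving this weight is substantial:

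- The affected outputs are descriptive, the study has one arm, and CGI-S is exploratory. No test rests on this step, and the tables report n, so the change in numbers is visible.
- The last-assessment row includes early terminators, so Week 52 is not the only on-treatment reference.
- Stopping effects have dedicated analyses: COWS from the subject's own end-of-treatment value (Section 3.7.8), post-discontinuation adverse events benchmarked on earlier severity (3.7.2), withdrawal events by exposure, including depression and anxiety terms (3.7.3, Appendix 3), and post-discontinuation C-SSRS (3.7.7).
- Laboratory, vital-sign and ECG outlier analyses exclude post-discontinuation values and are unaffected.
- Figure layout is left to separate mock-ups (Section 9), so whether a line will join Week 52 to follow-up is unknown.

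These points limit the importance; they do not remove the problem. A visible n shows that the set changed, not what the same subjects did. The last-assessment row includes people who never attend follow-up, so it is only a partial comparator. The COWS and adverse-event analyses show that the SAP already accepts an end-of-treatment reference; the four endpoint groups here lack one.

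A reader might go further and infer that Week 52 is completers only for every endpoint, that follow-up contains all early terminators, and that a false change is bound to appear. The documents do not support this. Section 6.1 places late terminators in the CGI-S Week 52 point, the protocol only asks or encourages terminators to return, and the artefact vanishes if the groups do not differ or, for safety data, if no terminator returns.

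**Conclusion.** The point holds as a conditional weakness in presentation and analysis. Week 52 and follow-up describe different subjects in one observed-data series, and for CGI-S, laboratory tests, vital signs and ECG no planned summary isolates within-subject change after treatment. An apparent shift can arise, or a real one be offset, if returning early terminators differ from completers.

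The mechanism follows from the text; the size does not. It is about s × d for safety data and generally smaller for CGI-S, where late terminators already sit in the Week 52 point. Every figure above rests on assumed completion, attendance and group differences and is illustrative. The adverse-event, COWS, C-SSRS and outlier results are not affected. The change is worth making because it is cheap and removes the ambiguity.

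**What to change.** In SAP Sections 3.6.2.3, 3.7.4.1, 3.7.5 and 3.7.6, add a summary of change from the subject's own last on-treatment (EOT or ET) value to each scheduled follow-up assessment, in subjects with both values:

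- CGI-S: Visits 16, 17 and 18.
- Vital signs and weight: Visits 15 to 18.
- Laboratory tests and ECG: Visit 18.

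Present it overall and separately for treatment completers and early terminators, within the existing prior-exposure groups. This follows the end-of-treatment baseline already used for COWS; state whether the two-day limit for an adequate COWS baseline also applies here.

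In the figures, do not join Week 52 to follow-up. Start the follow-up segment from the matched end-of-treatment mean of the subjects who contribute to it. The planned summaries against the study baseline can stay.

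The cost is a few extra descriptive tables, a change to the figure shells and some reprogramming. No new data, visits or protocol changes are needed.

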3.7. Safety Analysis

3.7.1. General Considerations

All safety endpoints will be summarized by prior ALKS 5461 exposure and overall based on observed data for the Safety Population.

3.7.2. Adverse Events

Adverse events will be coded by System Organ Class and Preferred Term using the Medical Dictionary for Regulatory Activities MedDRA version 19.0. The verbatim term will be included in the AE listings. An AE will be considered as a treatment emergent adverse event (TEAE) if it starts or worsens (if present at baseline) on or after the baseline during treatment period. An AE will be considered as a PDEAE if it starts or worsens during the Post-discontinuation Safety Period which is after the last dose date plus 1 day. For the determination of TEAEs during the treatment period, AEs with the greatest severity before the baseline will be used as the benchmark for the comparison of the AEs occurring during the treatment period. For PDEAEs, the greatest severity before or on the last dose date plus 1 day will be used as the benchmark for the comparison of the AEs occurring during the Post-discontinuation Safety Period.

All AEs will be listed by subject. TEAEs / PDEAEs, deaths, serious adverse events (SAEs), AEs leading to study discontinuation will be included in the summary tables. Summary tables will be provided by prior ALKS 5461 exposure and overall for the Safety Population. For AEs leading to study discontinuation or deaths, the AEs will be summarized in the period in which the discontinuation or death occurred. Drug related TEAEs include those scored as definitely related, probably related, and possibly related by the investigator.

The following summary tables will be produced for the treatment period / Post-discontinuation Safety Period by prior ALKS 5461 exposure and overall for the Safety Population:

- Overview AE summary tables (TEAEs / PDEAEs)
- TEAEs / PDEAEs by System Organ Class and Preferred Term
- TEAEs / PDEAEs by Preferred Term in decreasing frequency
- TEAEs / PDEAEs experienced by ≥5% of subjects (in any group) by Preferred Term
- TEAEs / PDEAEs by System Organ Class, Preferred Term, and Severity
- Drug-related TEAEs by System Organ Class and Preferred Term
- SAEs (fatal and non-fatal) by System Organ Class and Preferred Term
- SAEs (fatal and non-fatal) by Preferred Term in decreasing frequency
- AEs leading to study discontinuation by System Organ Class and Preferred Term
- AEs leading to study discontinuation by Preferred Term in decreasing frequency
- TEAEs by System Organ Class, Preferred Term, and Duration of Exposure
- TEAEs by Preferred Term in decreasing frequency and Duration of Exposure
- Duration of TEAEs experienced by ≥5% of All Subjects by Preferred Term

• Incidence of TEAEs experienced by ≥5% of All Subjects by Preferred Term and Exposure Interval

A subject having the same AE (as determined by the coded MedDRA preferred term) more than once will be counted only once in the calculation of the number and percentage of subjects for that AE. Similarly, if a subject has more than one AE in a System Organ Class, the subject will be counted only once in the number of subjects with an AE for that System Organ Class. If a subject has the same AE on multiple occasions, the highest severity (severe > moderate > mild) recorded for the event will be presented in the AE by severity summary. Similarly, if a subject has the same AE on multiple occasions, the closest relationship (related > not related, where related includes definitely related, probably related, and possibly related; and not related includes probably not related and definitely not related) recorded for the event will be presented in the AE by relationship summary. If a subject has the same AE on multiple occasions, the first presentation will be used in the incidence table and the longest duration will be used in the duration table.

The number and percentage of subjects with TEAE during the ALK5461-208 study will be summarized by System Organ Class, Preferred Term, and duration of exposure since the first dose of the study drug in the ALK5461-208 study (1 day to <1 month, \geq 1 to <3 months, \geq 3 to <6 months, \geq 6 to <9 months, \geq 9 to <12 months, and \geq 12 months). For each exposure interval, the percentage will be calculated as the number of subjects with a new TEAE that started during the exposure interval, relative to the number of subjects exposed during the interval. Separate tables for prior ALKS 5461 exposure and overall will be provided.

Descriptive statistics (number of subjects, mean, SD, median, 10th percentile, 90th percentile, minimum, and maximum) of duration (days) of TEAEs experienced by ≥5% of All Subjects will be provided by Preferred Term during treatment period for the Safety Population. The duration is defined as number of days from the TEAE start date to the TEAE stop date during the ALK5461-208 study, inclusive. If a TEAE is ongoing at the end of the treatment period, the TEAE stop date is imputed by last dose date plus 1 day. For those subjects who have the same event (same PT term) that is treatment emergent on multiple occasions, we will choose the longest duration as stated above. For partial TEAE start or stop date:

- If only day is missing but month available, TEAE start date will be imputed as the first day of the month and TEAE stop date will be imputed as the last day of the month.
- If both month and day are missing, TEAE start date will be imputed as the Visit 2 date or January 1st whenever applicable, and TEAE stop date will be imputed as the last dose date or December 31st whenever applicable.

The Incidence (%) of TEAEs experienced by $\geq 5\%$ of All Subjects by Preferred Term and Exposure Interval (1 day to <1 month, ≥ 1 to <3 months, ≥ 3 to <6 months, ≥ 6 to <9 months, ≥ 9 to <12 months, and ≥ 12 months) will be presented by prior ALKS 5461 exposure and overall during treatment period for the Safety Population. For those subjects who have the same event (same PT term) that is treatment emergent on multiple occasions, the first instance where that event was treatment emergent will be used, as stated above. The incidence (%) is calculated by n/m x 100%, where n is defined as the number of subjects with newly emergent or worsened adverse events during the exposure interval; m is defined as the number of subjects who had

treatment exposure during the exposure interval. The incidence (%) of TEAE over time will also be presented graphically. For each preferred term, a bar graph will be presented by prior ALKS 5461 exposure and overall. The number of n/m of three groups will be listed below the figure.

Subgroup analyses are planned for TEAEs only. Subgroups to include:

- Demographics (age [<55 years, ≥55 years], race [white, all other races], gender [female, male])
- Region (US, non-US)
- ADT class (SSRI, SNRI, and other)
- Benzodiazepines use (yes, no)
- Opioid use (yes, no)

A subject is considered as having used a Benzodiazepine (BDZ) or BDZ-like drug ("yes" subgroup) if the subject was taking any concomitant medication in the Benzodiazepine group for any duration in the treatment period of interest. A subject is considered as not having used a Benzodiazepine (BDZ) or BDZ-like drug ("no" subgroup) if the subject was not taking any concomitant medication in the Benzodiazepine group and sedating H1 antagonist group.

Similarly, a subject is considered as having used an opioid drug ("yes" subgroup) if the subject was treated with any concomitant medication in the opioid classification for any duration in the treatment period of interest. A subject is considered as not having used an opioid drug ("no" subgroup) if the subject was not treated with any concomitant medication in the opioid classification. A table of SAE by System Organ Class and Preferred Term for opioid use will be presented.

Subject listings for AEs will be included.

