3. DATA ANALYSIS

3.1. General Statistical Methodology

The safety and efficacy endpoints will be summarized by prior ALKS 5461 exposure: no prior exposure to ALKS 5461 and prior exposure to ALKS 5461, as well as overall.

Subjects with no prior exposure to ALKS 5461 come from three sources: De Novo (i.e., New Subjects), PLI Failures (i.e., antecedent study Prospective Lead-in Subjects Failures) and Placebo (i.e., those who did not receive any active treatment in an antecedent study).

Prior exposure to ALKS 5461 subjects include Continuing Subjects who received active treatment (doses ALKS 5461 0.5/0.5, ALKS 5461 1/1, or ALKS 5461 2/2) in an antecedent study. Subjects with prior exposure are designated as such independent of the duration of exposure in the antecedent trial.

In general, summary statistics (n, mean, standard deviation [SD], median, minimum, and maximum for continuous variables, and number and percentage of subjects in each category for categorical variables) based on observed data will be provided by prior ALKS 5461 exposure and overall. Measurements collected from unscheduled visits or repeated assessments will not be included in the by-visit summary tables or figures, but will be included in categorical outlier analyses of post-baseline values and subject listings.

In general, only data collected during the ALK5461-208 study will be summarized even though the baseline may come from an antecedent study.

Last assessment during treatment period, defined as the last non-missing value from scheduled post-baseline visit during the treatment period (i.e., from Visit 2 to Visit 14, inclusive), will be included in the by-visit summary tables for both efficacy and safety endpoints as appropriate.

Source data for the summary tables will be presented as subject data listings. Please refer to Section 6.1 on the handling of data collected at an early termination visit.

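### The TEAE duration table and the restricted interval-incidence table and bar graphs select terms on a pooled 5% cut-off, so a term common only in new users can lose its duration statistics and graph (minor)

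*SAP*

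**What the plan says.** SAP 3.7.2 lists the AE summaries, all to be shown by prior ALKS 5461 exposure and overall. Two different 5% rules appear in that list.

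- **Any-group rule.** The common-event table is "TEAEs / PDEAEs experienced by ≥5% of subjects (in any group) by Preferred Term".
- **Pooled rule.** Two later outputs are "Duration of TEAEs experienced by ≥5% of All Subjects by Preferred Term" and "Incidence of TEAEs experienced by ≥5% of All Subjects by Preferred Term and Exposure Interval". The text below the list repeats the pooled cut-off for both. It adds bar graphs of incidence over time for each preferred term, with the counts for three groups printed under each figure.

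The same list has two interval tables with no frequency cut-off: "TEAEs by System Organ Class, Preferred Term, and Duration of Exposure" and "TEAEs by Preferred Term in decreasing frequency and Duration of Exposure". They use the same six exposure intervals as the restricted table. Their percentages are "relative to the number of subjects exposed during the interval", and "Separate tables for prior ALKS 5461 exposure and overall will be provided".

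On data scope, SAP 3.1 states that in general "only data collected during the ALK5461-208 study will be summarized even though the baseline may come from an antecedent study". It defines the prior-exposed group as Continuing Subjects who received active drug in an antecedent study.

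**The concern.** The restricted interval outputs are displayed by group, but their rows are chosen on the pooled rate. The SAP gives no reason for departing from the any-group rule used earlier in the same list.

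The choice matters because the two groups are observed at different stages of treatment. Under Protocol 7.1.3, Continuing Subjects must have completed the antecedent treatment period, so those who stopped early cannot enter. Under Protocol 13.4, AE collection starts at consent for this study. Under Protocol 13.1, illnesses present before consent, which may include AEs from the earlier study, are recorded as medical history unless they worsen. Events from a prior-exposed subject's first-ever weeks on drug are therefore generally absent from the 208 counts, while the subject stays in the denominator.

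The dilution works against terms that are more frequent in new users than in prior-exposed subjects, which is the pattern expected of events at drug initiation. For such a term, how long the event lasts is a natural tolerability question, and the duration table is the only planned summary that answers it.

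**Working it through.** The 5% is a display rule, so there is no plan calculation to reproduce. The check is how far pooling can move a term across the cut-off.

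**Inputs**

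- Cut-off c = 5% (SAP 3.7.2).
- Planned N = 1,500 (SAP 2). I take the Safety Population as about that size, so the pooled cut-off is 0.05 × 1,500 = 75 subjects.
- f = share of subjects with no prior exposure; p = term rate in that group; q = term rate in prior-exposed subjects. None of the three is in the documents, so all are assumed and shown as ranges.

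**Formula**

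Pooled rate = f·p + (1 − f)·q. The term is dropped when this is below c, that is, when p < [c − (1 − f)·q] / f.

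**Limits with q = 1%**

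- f = 50%: (5 − 0.5)/0.5 = 9.0%
- f = 60%: (5 − 0.4)/0.6 = 7.7%
- f = 70%: (5 − 0.3)/0.7 = 6.7%
- f = 80%: (5 − 0.2)/0.8 = 6.0%

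These are break-even rates: a term exactly at the limit stays, and one below it goes.

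**Sensitivity to q** (same formula; entries are the new-user rate below which a term is dropped)

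| f (new users) | q = 0% | q = 1% | q = 2% | q = 3% | q = 5% |
|---|---|---|---|---|---|
| 50% | 10.0% | 9.0% | 8.0% | 7.0% | 5.0% |
| 60% | 8.3% | 7.7% | 7.0% | 6.3% | 5.0% |
| 75% | 6.7% | 6.3% | 6.0% | 5.7% | 5.0% |

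At q = 5% the limit equals the cut-off itself. From there upward, no term reaching 5% in new users can be dropped.

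**In counts, N = 1,500, f = 60%, q = 1%**

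- New users: 0.6 × 1,500 = 900. Prior-exposed: 600, with 0.01 × 600 = 6 events.
- 69 new users with the event: 69 + 6 = 75, and 75/1,500 = 5.0%. The term is kept.
- 68 new users: 68 + 6 = 74, and 74/1,500 = 4.9%. The term is dropped, although 68/900 = 7.6% of new users had it.

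**One term under two splits, p = 8%, q = 1%**

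- f = 50%: 60 + 7.5 = 67.5, and 67.5/1,500 = 4.5%. Dropped under the pooled rule, kept under the any-group rule.
- f = 75%: 90 + 3.75 = 93.75, and 93.75/1,500 = 6.25%. Kept under both.

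**What a dropped term loses, by output in SAP 3.7.2**

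| Information | Still reported elsewhere? |
|---|---|
| Overall frequency by group | Yes: full SOC/PT tables and the any-group table |
| Incidence by interval and group | Yes: the two tables with no cut-off |
| Row in the restricted interval table | No, but the same kind of information is in those two tables |
| Bar graph of incidence over time | No: the only planned graph of this kind |
| Duration statistics | No: the only planned duration table; otherwise subject listings |

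**The case against.** The strongest reply is that the timing information is already planned in full. The two interval tables without a cut-off cover every preferred term over the same six intervals, with separate tables by prior exposure. A reader might infer from the pooled rule that the time course of early events in new users would be missing from the report. The documents do not support that.

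A reader might also infer that initiation events as a class are the ones most likely to disappear. That goes too far. Only terms between 5% and the break-even rate are at risk. With q = 1% and an even split, anything in 9.0% or more of new users stays, so the most common initiation events are kept.

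The mechanism is not uniform either. Table 1 in Protocol 8.1 shows that subjects from study 205 enter off drug after a one-week discontinuation and titrate again within 208. Subjects on 1/1 from study 207 go to 2/2 on Day 1. Some start-of-treatment or dose-increase events in prior-exposed subjects are therefore counted in 208. That raises q and shrinks the effect, possibly to nothing.

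Finally, all these outputs are descriptive, no inference turns on the cut-off, and a pooled cut-off for supplementary displays is a defensible choice.

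All of this stands. It does not explain why one list uses two rules, and it does not restore the duration statistics or the graph for a term that the SAP itself would list as common.

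**Conclusion.** The point holds as a minor inconsistency. Under the pooled rule, a term in at least 5% of new users can appear in the common-TEAE table and still have no duration summary, no bar graph and no row in the restricted interval table. Its incidence by interval and by group is reported regardless.

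The size cannot be fixed from the documents. With q assumed at 1%, the terms at risk are those between 5% and 9.0%, 7.7%, 6.7% or 6.0% of new users for new-user shares of 50%, 60%, 70% or 80%. In the 60% case that means at most 68 of 900 new users with the event. The range narrows as the new-user share or q rises, and it is empty at q of 5% or more. The result also takes the pooled wording to mean the overall column of the Safety Population, which is its natural reading.

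**What to change.** In SAP 3.7.2, for the duration table, the restricted interval-incidence table and its bar graphs, select a term if it reaches 5% in at least one of three groups: prior exposure, no prior exposure, or overall. Change both the bullet list and the paragraphs below it that repeat the cut-off. This is the rule already used for the common-TEAE table, with the groups named.

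The cost is a change of wording in the SAP and the matching table shells, and a few more rows and figures. Data collection, endpoints and other analyses are unaffected.
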